### Subjects

Approximately 20 subjects are planned to be enrolled in and complete this study.

Potential subjects will be included if the following criteria are met: aged 40 - 80 years with a clinical diagnosis of stable, moderate-to-severe COPD (forced expiratory volume in 1 second [FEV1]  $\geq$ 30% and  $\leq$ 75% of predicted normal); spirometry-confirmed airflow obstruction (pre- and post-bronchodilator FEV1/FVC <0.70), a score of  $\geq$ 10 on the CATTM; a score of  $\geq$ 2 on the mMRC; taking inhaled (but not nebulized) LAMA+LABA or LAMA+LABA+ICS (capped at 10 subjects) for at least 8 weeks, and are able to use the standard jet nebulizer correctly.

Potential subjects with asthma or other significant lung disease, recent hospitalizations, or serious infections; are pregnant or breastfeeding; or are unsuitable to participate, as judged by the Investigator, will be excluded.

Refer to the complete eligibility list in Section 5.0.

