## 9.3.2 Statistical Analyses

Continuous endpoints will be summarized as change from baseline using a mixed model for repeated measures with model terms for time and background therapy, and with baseline included as a covariate. Within subject error will be modeled using an unstructured covariance matrix, and Kenward-Roger method will be used to estimate degrees of freedom. Least square mean estimates, standard errors, and corresponding 95% confidence limits will be presented at each post-treatment time of assessment.

Response frequencies will be summarized by negative binomial regression with model terms for time and background therapy, and with baseline included as a covariate. Within subject correlation in responder status will be modeled using an unstructured covariance matrix. Response proportions, standard errors, and corresponding 95% confidence limits will be generated from estimated frequencies and presented for each post-treatment time of assessment.

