# 5 Sample Size Justification

A sample size of approximately 20 subjects provides the ability to demonstrate a responder proportion estimate statistically differs from zero. Assuming a 30 percent response rate in the study population, 20 subjects would provide an expected count of 6 events. The two-sided 95% confidence interval for the number of events generated via normal approximation is (1.199, 10.801). Thus,20 subjects provide the ability to demonstrate the derived proportion differs from zero determined by the lower two-sided 95% confidence limit derived from the estimated count using a normal approximation assuming a standard error equal to the square root of 6.

Twenty subjects also provide the ability to demonstrate the estimates of mean change from baseline does not extend to the clinically meaningful deterioration limit of (+2 units). Assuming estimated mean improvement of 1 unit with a corresponding standard deviation equal to 4.5, 20 subjects provide the ability to demonstrate the upper 95% confidence interval for a mean change from baseline estimate does not exceed 2 units.

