# 8 Statistical Methods

### 8.1 General Reporting Conventions

Study data will be made available in listings or electronic format as requested. Study results will be reported in tabular form using descriptive and inferential statistics. Standard numeric descriptive statistics include number observed (n), mean, standard deviation (SD), median, minimum, and maximum values. Standard categorical descriptive statistics include the count and percentages of subjects for each level of the variable summarized. Confidence intervals (CIs) will be two-sided 95% intervals. Unless specified otherwise, two-sided p-values of less than or equal to 0.05 or one-sided p-values of less than or equal to 0.025 will be considered statistically significant. All summaries and statistical analyses will be completed using Version 9.4 or later of the SAS Statistical Analysis System (SAS Institute, Inc. Cary, NC) for Windows x64.

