### 8.3 Handling of Missing Data

As discontinuation of study medication will result in subject withdrawal, data collected after treatment withdrawal will not be included in the analyses, and missing data will not be imputed.

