### 8.4.5.2 Primary Efficacy Analysis

The FAS population will be used to assess the primary efficacy endpoint of proportion of CAT total score responders defined as improvement from baseline  $\geq 2$  at Week 12. The proportion of subjects classified as responders at week 12, standard errors, and corresponding 95% CI will be estimated by negative binomial regression with timepoint and background therapy (LABA+LAMA or LABA+LAMA+ICS) included as fixed effects, and with baseline CAT total score included as a covariate. The scale parameter in the negative binomial model will be held fixed by specifying a noscale option.

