### 8.4.5.3 Sensitivity and Supporting Analyses

As a supporting analysis the proportion of CAT total score responders defined as improvement from baseline  $\geq 2$  will be analyzed at Week 6 in the same manner as the primary efficacy analysis.

As a sensitivity analysis the primary efficacy endpoint analysis will also be analyzed with subject included as a repeated measure to provide a robust standard error for the estimated proportion and to accommodate model misspecification. The scale parameter in the negative binomial model will be held fixed by specifying a noscale option.

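### The SAP's primary responder model omits the within-subject correlation that the protocol specifies, so selective loss of Week 6 non-responders before Week 12 would bias the Week 12 proportion upward

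*SAP*

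**What the plan says.** Protocol 9.3.2 (repeated in the synopsis) gives the responder model terms for time, background therapy and baseline, and adds: "Within subject correlation in responder status will be modeled using an unstructured covariance matrix".

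SAP 8.4.5.2 keeps the three terms but not the correlation. The Week 12 proportion "will be estimated by negative binomial regression with timepoint and background therapy (LABA+LAMA or LABA+LAMA+ICS) included as fixed effects", with baseline CAT total score as covariate and the scale parameter held fixed at a value that is not given. No subject or repeated term appears.

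SAP 8.4.5.3 reruns this analysis as a sensitivity analysis "with subject included as a repeated measure to provide a robust standard error for the estimated proportion". It names no working correlation. SAP 2.2 lists no change from the planned analyses.

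On missing data, SAP 8.3 and protocol 9.3.6 exclude data collected after treatment withdrawal, and "missing data will not be imputed". The CAT is taken only at Visits 1, 3 and 4. The early-withdrawal visit in the schedule of activities has no CAT.

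**The concern.** A timepoint effect can be estimated only if both visits' records are in the model. Without a subject term, the two records of one person are then treated as if they came from two people.

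This matters mainly through missing data. Under protocol 7.1, a subject who permanently stops study medication is withdrawn. For anyone lost between Week 6 and Week 12, the Week 6 CAT is the only post-baseline efficacy observation. With no imputation, a modelled within-subject correlation is the only route by which that observation can inform the Week 12 estimate. Under independence the Week 12 estimate rests on those still present. If the people who leave are mostly Week 6 non-responders, and status persists between visits, those still present respond more often than the whole group.

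Selective loss is possible on the protocol's own terms: section 7.1.5 lists lack of efficacy among possible reasons for discontinuation, and 7.1.3 allows withdrawal after an exacerbation. The responder proportion is the primary endpoint, and protocol 9.1 bases conclusions on estimates and intervals. The SAP keeps an unstructured matrix for the secondary change-from-baseline model (8.4.6.1), so the primary endpoint gets the weaker handling, with no reason given.

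**Working it through.** **The plan's own figure.** "Assuming a 30 percent response rate in the study population, 20 subjects would provide an expected count of 6 events" (SAP 5). With the stated standard error √6 = 2.449, the interval for the count is 6 ± 1.960 × 2.449 = (1.199, 10.801), which is 6.0% to 54.0% of 20. This reproduces the SAP exactly.

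**Inputs.** From the documents: responder rate p = 0.30, about 20 subjects, two-sided 95% intervals, no imputation. Assumed, because the documents give no figure: the Week 6 to Week 12 correlation of responder status, ρ = 0.3 to 0.7; the share d0 of Week 6 non-responders lost before Week 12, 10% to 30%; the share d1 of Week 6 responders lost, 0 unless stated. The true rate is taken as p at both visits, and loss depends only on Week 6 status.

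**Closed form.** 
- P(respond at 12 | responder at 6) = p + (1−p)ρ
- P(respond at 12 | non-responder at 6) = p − pρ
- Proportion among those observed at Week 12 = [p(1−d1)(p+(1−p)ρ) + (1−p)(1−d0)(p−pρ)] / [p(1−d1) + (1−p)(1−d0)]

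With ρ = 0.5, d0 = 0.20 and d1 = 0, the conditional rates are 0.65 and 0.15. The result is (0.30 × 0.65 + 0.56 × 0.15) / (0.30 + 0.56) = 0.279 / 0.86 = 32.4%, or +2.4 points.

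Bias in points at p = 0.30, d1 = 0:

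| ρ | d0 = 10% | d0 = 20% | d0 = 30% |
|---|---|---|---|
| 0.3 | +0.7 | +1.5 | +2.4 |
| 0.5 | +1.1 | +2.4 | +4.0 |
| 0.7 | +1.6 | +3.4 | +5.6 |

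The bias is zero when d0 = d1 or ρ = 0. If responders leave instead (d1 = 0.20, d0 = 0, ρ = 0.5), the result is (0.24 × 0.65 + 0.70 × 0.15) / 0.94 = 0.261 / 0.94 = 27.8%, or −2.2 points.

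**Does modelling the correlation recover the rate?** Simulation: log link, dispersion fixed at 1 and at 0 (the SAP states neither link nor value), ρ = 0.5, d0 = 20%, n = 2,000, six data sets for each setting. With two visits an unstructured correlation is a single parameter, so an exchangeable fit is equivalent.
- Dispersion 1: independent records 33.6%, correlation modelled 30.9%.
- Dispersion 0: independent records 32.1%, correlation modelled 29.5%.

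Six data sets leave some noise around the true 30%, but the gap between fits is 2.6 points in both settings, close to the closed-form 2.4. A repeated-subject fit with working independence gave the same point estimate as the independent-records model in every scenario.

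**Width of the Week 12 interval.** At n = 20 with no loss, the mean log-scale standard error of the independent-records model is 0.52 (dispersion 1) or 0.45 (dispersion 0). The robust standard error is about 0.38.

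**Loss before Week 6.** These subjects have no post-treatment CAT and fall outside the FAS. If 2 non-responders of 20 leave this early, the estimate is 6/18 = 33.3% against 6/20 = 30%; if 3 leave, 6/17 = 35.3%. No correlation structure changes this.

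**The case against.** The strongest case against acting is that the bias is hypothetical and small. The protocol intends that "Approximately 20 subjects are planned to be enrolled in and complete this study", and neither document gives a drop-out rate or links drop-out to response. With 20 complete subjects and a 30% rate, the binomial standard deviation is √(0.30 × 0.70 / 20) = 10.2 points, larger than any bias in the table. A simulation at n = 20 used the sample-size section's mean change of −1 and SD of 4.5 (a responder rate of about 46%) and lost 30% of Week 6 non-responders and no responders. The root mean squared error was 13.7 points under independence and 13.5 with the correlation modelled at a visit correlation of 0.5, and 14.3 against 13.7 at 0.7. The correlated fit can also fail: in the negative binomial form, with assumed log link and dispersion 1, it did not converge in about 1% to 8% of trials at n = 20. A simpler model without covariates had no failures.

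All of that stands. It limits the size of the point and argues for a stated fallback. It does not answer the discrepancy, which exists whatever the drop-out. Nor does sampling noise excuse a systematic shift that one model statement would largely remove under these assumptions.

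Some stronger readings are tempting but unsupported:
- A reader might infer that the SAP abandons the correlation altogether. SAP 8.4.5.3 does bring subject in; its working correlation is unnamed, not stated to be independence.
- Counting 20 subjects as up to 40 records might suggest a Week 12 interval that is too narrow. The standard errors above show the reverse.
- The Type 3 table (14.2.1.2) might seem at risk. Background therapy is an adjustment term with no hypothesis attached, so nothing is claimed here.

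**Conclusion.** The SAP's primary responder analysis departs from protocol 9.3.2 without declaring it, and the sensitivity analysis does not clearly restore the protocol's model. That much follows from the text alone.

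The effect on the estimate is conditional. At a 30% rate, with a visit correlation of 0.3 to 0.7 and 10% to 30% of Week 6 non-responders (and no responders) lost before Week 12, the Week 12 proportion is biased upward by about 0.7 to 5.6 points. The correlations and loss rates are assumptions. It would go too far to say that the reported proportion will be inflated: there is no bias with complete data or non-selective loss, and the bias is downward if responders leave.

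The success decision in SAP 8.4.5.1 (lower limit above 0) does not change. With a log link, the usual choice but not stated in the SAP, the back-transformed lower limit is above 0 whenever the model can be fitted. The remedy works only for subjects with a Week 6 CAT, and the calculation assumes that loss depends on Week 6 status alone.

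**What to change.** In SAP 8.4.5.2:
- Fit the Week 6 and Week 12 responder model with subject as the repeated unit and an unstructured (two-visit) working correlation estimated from the data.
- Take the Week 12 proportion, its standard error and its 95% CI from that fit.
- State the fallback if it does not converge: working independence with a robust standard error. SAP 8.4.6.1 already provides a fallback for the secondary model.

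In SAP 8.4.5.3, keep the independence fit as the sensitivity analysis and name the working correlation. In SAP 2.2, record any departure from protocol 9.3.2 that is retained.

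The cost is SAP wording and one model statement. The downside is one extra parameter and a small risk of non-convergence at about 20 subjects. Loss before Week 6 is a question of FAS definition and missing-data handling and needs separate treatment, for example an analysis that counts a missing CAT as non-response.

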### 8.4.5.3 Sensitivity and Supporting Analyses

As a supporting analysis the proportion of CAT total score responders defined as improvement from baseline  $\geq 2$  will be analyzed at Week 6 in the same manner as the primary efficacy analysis.

As a sensitivity analysis the primary efficacy endpoint analysis will also be analyzed with subject included as a repeated measure to provide a robust standard error for the estimated proportion and to accommodate model misspecification. The scale parameter in the negative binomial model will be held fixed by specifying a noscale option.

# 8.4.6 Secondary Efficacy Endpoint

### 8.4.6.1 Change from Baseline CAT Total Score

The secondary endpoint of change from baseline in CAT total score will be evaluated at Week 6 and Week 12. Scores for the CAT total score ranges from 0-40. CAT total score will be summarized descriptively at baseline and each timepoint. A mixed model for repeated measures with timepoint and background therapy (LABA+LAMA or LABA+LAMA+ICS) included as fixed effects, and with baseline CAT total score included as a covariate. Subject will be included as a random effect and an unstructured covariance matrix will be used. The Kenward-Rogers approximation will be used for the denominator degrees of freedom. In the event the model fails to converge, a compound symmetry covariance structure, an ANCOVA model at each timepoint will be performed with background therapy included as a fixed effect and baseline

Statistical Analysis Plan	Client/Project	Verona Pharma/RPL554-CO-303
	Version and Date	V02 12/11/2024

CAT total score included as a covariate. Least square mean estimates, standard errors, and corresponding 95% confidence limits will be presented for each post-treatment time of assessment. A plot of the least square means change from baseline in total score over time will be presented.

### 8.4.6.2 Change from Baseline CAT Individual Item Analyses

The CAT questionnaire contains 8 individual items with scores ranging from 0-5. Each individual item will be summarized at Week 6 and Week 12 in the same manner as the change from baseline CAT Total Score secondary efficacy endpoint. The baseline for individual items is the item score at the baseline assessment. Least square mean estimates, standard errors, and corresponding 95% confidence limits will be presented at each post-treatment time of assessment

### 8.4.7 Safety Evaluations and Analyses

All safety evaluations will be conducted on the safety population. Safety analyses will include incidence of adverse events and vital sign summaries.

### 8.4.7.1 Adverse Events and SAEs

An adverse event (AE) is any untoward medical occurrence in a subject or subject, temporally associated with the use of study medication, whether considered related to the study medication or not. AEs will be collected from time of first dose to follow-up contact. Medical and COPD condition(s) identified during screening will be documented as medical history and not as an AE unless the condition worsens during the study and meets the definition of an AE. Treatment-emergent adverse events (TEAE) are any events that occur after the first dose of study treatment. Serious adverse events (SAE) include any occurrence defined as an AE that results in any of the following:

- Death
- Is life-threatening
- Requires in-patient hospitalization or prolongation of hospitalization
- Results in persistent disability/incapacity
- Is a congenital anomaly/birth defect
- Other

AEs requiring hospitalization include any events at a hospital or emergency ward for observation and/or treatment that would not have been appropriate in the physician's office or outpatient setting. Complications that occur during hospitalization are AEs. Hospitalization for elective treatment of a pre-existing condition that did not worsen from baseline is not considered an AE. For the "Other" criteria for SAEs, medical or scientific judgment should be exercised in deciding whether SAE reporting is appropriate in other situations such as important medical events that may not be immediately life-threatening or result in death or hospitalization but may jeopardize the subject or may require medical or surgical intervention to prevent one of the other outcomes listed in the above definition. These events should usually be considered serious.

Statistical Analysis Plan	Client/Project	Verona Pharma/RPL554-CO-303
	Version and Date	V02 12/11/2024

In addition to seriousness, AEs will be classified based on intensity (mild, moderate, severe), and relatedness/causality (reasonable possibility or no reasonable possibility). AEs will be coded using the Medical Dictionary for Regulatory Activities (MedDRA) and summarized by system organ class (SOC) and preferred term (PT). TEAEs, for the Safety Analysis Set, will be listed and summarized descriptively as the count and percentage of subjects experiencing the event in tabular form. Seriousness, relatedness, and outcome will be identified in the listings. AE summaries will include the following:

- Overall TEAE Summary
- TEAEs by SOC and PT
- Serious TEAEs by SOC and PT
- Treatment-related TEAEs by SOC and PT
- Serious treatment-related TEAEs by SOC and PT
- TEAEs by Severity and SOC and PT
- TEAEs Resulting in Discontinuation of Study Medication by SOC and PT
- TEAEs Resulting in Withdrawal from Study by SOC and PT
- TEAEs Resulting in Death by SOC and PT
- Listing of all TEAEs
- Listing of all Serious TEAEs
- Listing of all TEAEs Resulting in Death
- Listing of all TEAEs Resulting in Discontinuation of Study Medication
- Listing of all TEAEs Resulting in Withdrawal from Study

Adverse events will be counted once per patient per SOC and PT. Incidence of TEAEs will be presented by SOC and PT and broken down further by maximum severity and relationship to study medication. Severity is classed as mild/moderate/severe (increasing severity). TEAEs starting after the first dose of study medication with a missing severity will be classified as severe. If a patient reports a TEAE more than once within that SOC/ PT, the AE with the worstcase severity will be used in the corresponding severity summaries. Relationship to Study Medication, as indicated by the Investigator, is classed as "unknown", "unrelated", "unlikely to be related", "possibly related" and "probably related" (increasing probability of relationship). A "related" TEAE is defined as a TEAE with a relationship to study medication as "possibly related" or "probably related" to study medication. TEAEs with a missing relationship to study medication will be regarded as "probably related" to study medication. If a patient reports the same AE more than once within that SOC/ PT, the AE with the worst-case relationship to study medication will be used in the corresponding relationship summaries. TEAEs leading to discontinuation of study medication are AEs recorded as "Study Treatment Permanently Discontinued" on the "Adverse Events" page of the eCRF. Serious adverse events (SAEs) are those events reported as "Serious" in "Adverse Events". TEAEs leading to Death are those events reported as "Fatal".

### 8.4.7.2 Vital Signs

Vital signs will be collected at Day 1, Week 6, and Week 12 visits and will include blood pressure and pulse rates. Vital signs, for the Safety Analysis Set, will be summarized

Statistical Analysis Plan	Client/Project	Verona Pharma/RPL554-CO-303
	Version and Date	V02 12/11/2024

descriptively in tabular format as the values at each visit and change from baseline values for each parameter. Vital sign measurements will also be included in listing format. Abnormal and markedly abnormal values will be identified in the vital sign listings. Markedly abnormal values are defined in Table 2.

Table 2: Markedly	Abnormal	Post-Baseline	Vital Signs
I abic 2. Markenry		i ost Dasenne	v itai Sigiis

Variable	Unit	Abnormally Low	Abnormally High
SBP	mmHg	
 
A decrease from Baseline of ≥ 40
 
Value ≤ 90
 
	
 
An increase from Baseline of ≥ 40
 
Value ≥ 180
 

DBP	mmHg	
 
A decrease from Baseline of ≥ 20
 
Value ≤ 50
 
	
 
An increase from Baseline of ≥ 20
 
Value ≥ 105
 

Pulse Rate	Bpm	
 
A decrease from Baseline of ≥ 30
 
Value ≤ 50
 
	
 
An increase from Baseline of ≥ 30
 
Value ≥ 110
 

### 8.4.7.3 Physical Examination

A brief physical exam will be conducted on the Day 1 visit and will include assessments of the cardiovascular, respiratory, gastrointestinal, and neurological systems. Physical examination results, for the Safety Analysis Set, will be provided in listing format.

### 8.4.7.4 Pregnancy Test Results

Urine pregnancy tests will be conducted at the Day 1, Week 6, and Week 12 visits on women of childbearing potential only. Urine pregnancy test results, for the Safety Analysis Set, will be provided in listing format.

Client/Project	Verona Pharma/RPL554-CO-303
Version and Date	V02 12/11/2024

# 10 List of Tables, Figures and Listings

Table	Title	Population
Number		
14.1.1	Study Enrollment	All Subjects
14.1.2	Subject Disposition	SAS Subjects
14.1.3	Protocol Deviations	SAS Subjects
14.1.3	Demographics and Baseline Characteristics	SAS Subjects
14.1.4	Medical History	SAS Subjects
14.1.5	Smoking History	SAS Subjects
14.1.6	COPD History	SAS Subjects
14.1.7.1	Prior Medications by ATC Levels 1, 2, and 4	SAS Subjects
14.1.7.2	Concomitant Medications by ATC Levels 1, 2, and 4	SAS Subjects
14.1.8	Treatment Compliance	SAS Subjects
14.2.1.1	Proportion of CAT Responders at Week 12	FAS Subjects
14.2.1.2	Analysis of Type 3 Model Effects on CAT	FAS Subjects
	Responder Status at Week 12	
14.2.1.3	Proportion of CAT Responders at Week 6	FAS Subjects
14.2.1.4	Sensitivity Analysis of Proportion of CAT	FAS Subjects
	Responders at Week 12	
14.2.2.1	Change From Baseline in CAT Total Score by	FAS Subjects
	Timepoint	
14.2.2.2	Change From Baseline in CAT Individual Item	FAS Subjects
	Scores by Timepoint	
14.3.1.1	Overall Summary of Treatment-Emergent Adverse	SAS Subjects
	Events	
14.3.1.2	Treatment-Emergent Adverse Events by System	SAS Subjects
	Organ Class and Preferred Term	
14.3.1.3	Serious Treatment-Emergent Adverse Events by	SAS Subjects
	System Organ Class and Preferred Term	
14.3.1.4	Treatment-Related Treatment-Emergent Adverse	SAS Subjects
	Events System Organ Class and Preferred Term	
14.3.1.5	Serious Treatment-Related Treatment-Emergent	SAS Subjects
	Adverse Events by System Organ Class and	
	Preferred Term	
14.3.1.6	Treatment-Emergent Adverse Events by Severity	SAS Subjects
	and System Organ Class and Preferred Term	
14.3.1.7	Treatment-Emergent Adverse Events Resulting in	SAS Subjects
	Discontinuation of Study Medication by System	
	Organ Class and Preferred Term	

Statistical Analysis Dlan	Client/Project	Verona Pharma/RPL554-CO-303
Statistical Analysis Plan	Version and Date	V02 12/11/2024

14.3.1.8	Treatment-Emergent Adverse Events Resulting in Withdrawal from Study by System Organ Class and Preferred Term	SAS Subjects
14.3.1.9	Treatment-Emergent Adverse Events Resulting in Death by System Organ Class and Preferred Term	SAS Subjects
14.3.2	Summary of Vital Signs Change from Baseline by Timepoint	SAS Subjects

Listing	Title	Population
Number		-
16.1.1	Study Enrollment and Disposition	All Subjects
16.1.2	Screen Failures and Reason for Failure	All Subjects
16.1.3	Major Protocol Deviations	SAS Subjects
16.1.4	Demographics and Baseline Characteristics	SAS Subjects
16.1.5	Medical History	SAS Subjects
16.1.6	Smoking History	SAS Subjects
16.1.7	COPD History	SAS Subjects
16.1.8.1	Prior Medications	SAS Subjects
16.1.8.2	Concomitant Medications	SAS Subjects
16.1.9	Treatment Compliance	SAS Subjects
16.1.10	Modified Medical Research Council (mMRC)	SAS Subjects
	Dyspnea Scale Results	
16.2.1	CAT Total Score Results by Timepoint	FAS Subjects
16.2.2	CAT Individual Item Score Results by Timepoint	FAS Subjects
16.3.1.1	Treatment-Emergent Adverse Events	SAS Subjects
16.3.1.2	Serious Treatment-Emergent Adverse Events	SAS Subjects
16.3.2	Vital Sign Results	SAS Subjects
16.3.3	Physical Exam Results	SAS Subjects
16.3.4	Urine Pregnancy Test Results	SAS Subjects

Figure Number	Title	Population
14.2.1	Plot of CAT Total Score LSM Change from Baseline Over Time	FAS Subjects

